***Contraception***

21. Refer to [Appendix D](#) for reproductive criteria for male and female patients. Female patients of childbearing potential must have a negative serum beta-human chorionic gonadotropin pregnancy test result at screening and at baseline before the first study drug administration

**6.3. Exclusion Criteria**

Patients who meet any of the following criteria may not be enrolled:

***General***

1. Investigator site staff directly involved in the conduct of the study and their family members, site staff otherwise supervised by the investigator, and sponsor and sponsor delegate employees directly involved in the conduct of the study and their family members

***Cardiovascular System***

2. History of acute coronary syndromes, including myocardial infarction, coronary artery bypass graft, unstable angina, coronary angioplasty or stenting within 24 weeks prior to first administration of study drug
3. History of or current Class II, III or IV heart failure as defined by the New York Heart Association (NYHA) functional classification system or symptomatic or poorly-controlled cardiac arrhythmia

4. Uncontrolled or poorly-controlled hypertension (defined as systolic blood pressure >160 mm Hg) for more than four weeks despite optimal medical management

***General and Infectious Disease***

5. Child-Pugh Class C
6. Any comorbidity or concomitant medical or other condition that in the opinion of the Investigator and/or Sponsor Medical Monitor renders the patient unsuitable for participation in the trial or unlikely or unable to fully comply with study procedures, restrictions and/or requirements that are considered relevant for the evaluation of the efficacy or safety of the trial drug  
Consideration should be given to lack of currently-available immunoprotection against SARS-CoV-2 as a condition that may render a patient unsuitable for participation in the trial or unlikely or unable to fully comply with study procedures, restrictions and/or requirements that are considered relevant for the evaluation of the efficacy or safety of study treatment
7. Uncontrolled intercurrent illness, including active or chronic infection requiring systemic therapy or oral or systemic antibiotics within 14 days prior to study start
8. History of non-viral hepatitis or cirrhosis, alcohol abuse or active tuberculosis
9. Administration of live attenuated vaccines within 28 days prior to start of treatment or anticipated need for vaccination with live attenuated vaccine during the study
10. Major surgery within 28 days of scheduled Cycle 1 Day 1 dosing or minor surgery within seven days prior to initiation of study treatment or elective or planned major surgery to be performed during the course of the clinical trial

***CNS Disease Considerations***

11. History or evidence of known CNS metastases or carcinomatous meningitis; patients with previously treated brain metastases may participate provided they are stable (without evidence of progression by imaging for at least four weeks prior to the first dose of trial treatment and any neurologic symptoms have returned to baseline), have no evidence of new or enlarging brain metastases, and are not using steroids for at least seven days prior to trial treatment; this exception does not include carcinomatous meningitis which is excluded regardless of clinical stability

***Coagulation Considerations***

12. Chronic therapy with nonsteroidal anti-inflammatory drugs (NSAIDs; e.g., indomethacin, ibuprofen, naproxen or similar agents) or other anti-platelet agents (e.g., clopidogrel, ticlopidine, dipyridamole, anagrelide); aspirin up to 325 mg per day is permitted
13. Significant bleeding disorders, vasculitis or a significant bleeding episode from the GI tract within three months prior to study entry

***Immune System***

14. History of severe hypersensitivity reactions to antibodies
15. Systemic steroid therapy (>10 mg daily prednisone or equivalent) or any other form of immunosuppressive therapy within seven days prior to the first dose of study treatment; topical, inhaled, nasal and ophthalmic steroids are not prohibited
16. History of autoimmune disease that has required systemic treatment with disease-modifying agents, corticosteroids, or immunosuppressive drugs unless in the opinion of the investigator the patient is in

a complete and durable remission; physiologic replacement therapies, such as thyroxine, insulin, or physiologic corticosteroid replacement therapy for adrenal or pituitary insufficiency, is allowed

17. Prior organ transplantation including allogeneic or autologous stem cell transplantation

### **Oncology**

18. Concurrent or previous other malignancy within two years of study entry with the exception of cured basal or squamous cell skin cancer, superficial bladder cancer, prostate intra-epithelial neoplasm, carcinoma *in situ* of the cervix, or other non-invasive or indolent malignancy

19. Concurrent enrollment in another therapeutic clinical study

20. Prior treatment with anti-CD47 or anti-SIRP $\alpha$  therapy

21. Prior radiation to mediastinal/periocardial region

### **6.4. Re-Screening**

A subject who fails to qualify for the study based on laboratory tests may be considered for re-screening at the discretion of the Investigator and after consultation with the Sponsor Medical Monitor if it is considered that the subject status has changed and the subject may now qualify for the study. Screening is limited to two attempts (initial screening and one re-screening attempt).

### **6.5. Waivers of Inclusion/Exclusion Criteria**

In general, waivers of inclusion or exclusion criteria will not be granted; the Investigator may consult with the Sponsor Medical Monitor on a case-by-case.

### **6.6. Patients or Partners of Patients of Reproductive Potential**

This is an exclusion criterion and women of child-bearing potential must not be considering becoming pregnant during the study.

All women of childbearing potential who participate in the study should be counseled on the need to practice adequate birth control and on the importance of avoiding pregnancy during study participation. Women should be instructed to contact the investigator or study staff immediately if pregnancy occurs or is suspected.

Pregnancy testing will be conducted prior to administration of IP and throughout study participation on every woman of childbearing potential. A woman who is found to be pregnant at the Screening Visit will be excluded from the study and considered to be a screening failure.

A serum pregnancy test is required at screening. Following screening, pregnancy tests may be urine or serum tests, and must have a sensitivity of at least 25 mIU/mL. Pregnancy tests will be performed in WOCBP at the times listed in the Schedule of Assessments (Table 24). Following a negative pregnancy test result at screening, appropriate contraception must be commenced and a second negative pregnancy test result will be required at the baseline visit prior to the patient receiving the study treatment. Pregnancy tests will also be done whenever one menstrual cycle is missed during the active treatment period (or when potential pregnancy is otherwise suspected) and at the end of the study. Pregnancy tests may also be repeated if requested by IRBs/ECs or if required by local regulations. If a urine test cannot be confirmed as negative (e.g., an ambiguous result), a serum pregnancy test is required. In such cases, the patient must be excluded if the serum pregnancy result is positive.

Patients will be instructed to notify the Investigator if pregnancy is discovered either during or within 45 days of the last dose of study treatment TTI-621 (or as per USPI for doxorubicin combination treatment), which corresponds to the time needed to eliminate any reproductive safety risk of the study intervention(s).

#### **6.7. Provisions for Enrollment of Additional Patients based on Emerging Data**

Because this study has a relatively small sample size and patient heterogeneity may impact on interpretation of safety, clinical activity and/or other study objectives, provision is made that additional patients may be enrolled under certain conditions in order to have a sufficient number of patients to support the planned study objectives.

- It is intended that each patient will receive six cycles of doxorubicin as fewer than six cycles has been shown to provide less benefit to the patient compared to six or more cycles. If emerging data suggests that reduced exposure to doxorubicin has an impact on patient outcome with combined with TTI-621, additional patients may be enrolled to support an evaluation of TTI-621 when combined with doxorubicin for six cycles.
- If emerging data suggests that safety, activity or other study objective is different for patients who have received prior treatment versus no prior treatment, the inclusion criterion may be modified or additional patients may be enrolled to generate a more homogenous patient population.
- If emerging data suggest other patient characteristics may impact on safety, activity or other study objective, additional patients may be enrolled to more fully investigate the observation.

**7. ENROLLMENT PROCEDURE AND METHOD OF ASSIGNING SUBJECTS TO TREATMENT GROUPS****7.1. Enrollment Procedure**

At the time a prospective subject signs the informed consent form, a unique subject number will be assigned and the appropriate portion of a Registration/Enrollment form will be completed and sent to the Sponsor or designee. Subjects will be screened for eligibility according to the criteria outlined in [Section 6](#). Once a subject is deemed eligible, the completed Registration/Enrollment form will be sent to the Sponsor or designee, at which time the TTI-621 dose level and cohort or expansion arm will be assigned.

**7.2. Method of Assigning Subjects to Treatment Groups**

The dose escalation portion of the study carries a traditional 3+3 design to evaluate three dose levels of TTI-621. Standard guidelines for enrollment for the 3+3 design will be followed, with requirement that three patients complete the 21-day safety assessment period before the next dose cohort is open to enrollment and expansion to six patients in the case of a treatment-related dose-limiting toxicity.

However, recognizing that leiomyosarcoma is a rare disease and expecting that patients with leiomyosarcoma may be eager to participate in the study, careful modifications to the enrollment schema have been developed to avoid having to withhold enrollment for these patients. During the dose escalation portion of the study, eligible patients will be enrolled to the cohort that is open at the time they present to the study. Based on known safety and clinical activity of the lowest planned dose of TTI-621, 0.2 mg/kg, gleaned from other ongoing clinical trials, it is anticipated that this dose will serve as the TTI-621 dose level for Cohort A. Thus, expansion Cohort A will open to enrollment once that dose level is judged to be safe in the dose escalation portion of the study; if a dose escalation cohort and expansion Cohort A are open to enrollment at the same time, priority for enrollment will be given to the dose escalation cohort and enrollment into expansion Cohort A will be limited to those patients who present to the study after enrollment to an escalation cohort is closed and meet all the eligibility criteria for the expansion portion of the study (including documentation of the leiomyosarcoma indication).

When both expansion cohorts are open to enrollment, assignment of eligible patients will be made on an alternating basis, with cohort assignment made by the CRO overseeing the study on behalf of the sponsor independent of investigator input and based strictly on chronology of verification of eligibility of patients as they complete screening assessments.

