## 2. SYNOPSIS

Protocol Number	TTI-621-03
Version and Date	2.0, 17 June 2022
Phase of Clinical Development	Phase I/II
Protocol Title	A Phase I/II Study of TTI-621 in Combination with Doxorubicin in Patients with Unresectable or Metastatic High-Grade Leiomyosarcoma
Investigational Product	TTI-621 (SIRP $\alpha$ -IgG1 Fc)
IND Number	129118
Study Population	Patients aged 18 years or older with unresectable or metastatic leiomyosarcoma who have not received prior treatment with anthracyclines (dose expansion); patients with leiomyosarcoma, undifferentiated pleomorphic sarcoma, myxofibrosarcoma, dedifferentiated liposarcoma, angiosarcoma or epithelioid sarcoma will be allowed to enroll into the dose escalation portion of the study.
General Investigative Plan	A dose escalation will be undertaken in anthracycline-naïve patients with the high grade soft tissue sarcomas subtypes of leiomyosarcoma, undifferentiated pleomorphic sarcoma, myxofibrosarcoma, dedifferentiated liposarcoma, angiosarcoma or epithelioid sarcoma to evaluate safety of the planned dosing regimen of doxorubicin at 75 mg/m  in combination with TTI-621. The study will then be expanded to evaluate clinical activity and safety of TTI-621 at two dose levels in combination with doxorubicin at 75 mg/m  in patients with high-grade leiomyosarcoma.
Investigative Sites	Up to 20 centers in the US
Planned Number of Subjects	Up to approximately 80, including up to approximately 18 in the dose escalation portion of the study and approximately 62 subjects in the expansion portion of the study
Enrollment Period	The enrollment period is anticipated to be approximately 18 months in duration, with the first patient anticipated to be enrolled in July 2021 and completion of enrollment anticipated for December 2022
Background and Rationale	Soft tissue sarcomas are a rare, heterogeneous group of mesenchymal tumors, commonly the result of complex chromosomal abnormalities that play a role in disease progression and metastasis.  Doxorubicin has been since the 1970s the standard of care for first-line treatment of patients with metastatic or advanced soft tissue sarcoma; however,

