In an ongoing clinical trial of TTI-621 in patients with relapsed or refractory hematologic malignancies and selected solid tumors (NCT02663518), as of 01 October 2020, 235 patients have been enrolled to evaluate escalating dose levels of TTI-621 and in combination with other treatment regimens. In this study, TTI-621 is administered weekly and doses ranging from 0.05 mg/kg to 2.0 mg/kg have been evaluated. The safety profile is very similar across dose levels, with the primary Grade  $\geq 3$  treatment-related adverse event being acute but reversible thrombocytopenia which occurred in 22% of patients treated at dose levels of 0.05 mg/kg up to 0.5 mg/kg alone and in combinations and in 24% of patients treated at dose levels ranging from 0.5 mg/kg up to 2.0 mg/kg. Among patients with T cell lymphomas treated with TTI-621 at a dose of 0.2 mg/kg, an overall response rate of 21% has been observed in the intent-to-treat patient. At higher dose levels, up to 2.0 mg/kg, experience is more limited as this portion of the study is still ongoing. As of 12 April 2021, a 19% response rate has been observed in the intent-to-treat population of patients with cutaneous T cell lymphoma at dose levels between 0.7 mg/kg and 2.0 mg/kg; five patients continue to receive treatment with TTI-621 at 2.0 mg/kg and this portion of the study remains open to enrollment.

[figure not shown]
Thus, given the powerful rationale that supports CD47-targeted immune-based therapy in sarcoma, this study will now evaluate TTI-621 in patients with advanced high-grade leiomyosarcoma, one of the most common soft tissue sarcoma subtypes. As a first step, the safety and activity of escalating doses of TTI-621 in combination with doxorubicin administered under the medically-recognized standard dosing regimen (75 mg/m^2 on Day 1 of 21-day cycles for up to six cycles) will be evaluated in the first part of this study, with expansion cohorts to evaluate the safety and activity of a high dose and a low dose of TTI-621 in combination with doxorubicin with the goal of identifying the optimal combination for subsequent clinical evaluations.

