### **8.4. Blinding of Treatment**

This is an open-label study; study treatments will not be blinded.

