### **13.8. Overview of Safety Monitoring**

Throughout the study, investigators, site staff and the study Sponsor will meet regularly to review the status of all active patients on study. During the dose escalation portion of the study, a weekly safety and information call will be held with participating investigators and site staff to discuss safety, review any questions, provide updates and to share information across sites. At the completion of each dose escalation cohort, safety data will be summarized and presented for discussion with all investigators for the purpose of determining whether the observed safety in each cohort warrants escalation to the next higher dose level or whether an alternate dose level or other action should be considered.

During the dose expansion portion of the study, these regularly-scheduled safety and information calls will continue; the calls will initially be held at two-week intervals although *ad hoc* meetings may be held

as necessary to review specific safety or other issues that might arise during the course of the study. As the study progresses, the frequency of these safety and information calls may be adjusted to reflect need on the basis of safety observations observed, the rate of enrollment and investigator or Sponsor request or need.

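### While both expansion cohorts are open, A/B assignment alternates and so can be predicted; central randomisation by the same CRO would reduce this, and the SAP should label any A-versus-B display as non-randomised and flag non-concurrent patients

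*Protocol*

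**What the plan says.** **Allocation.** Under Protocol 7.2, while both expansion cohorts are open, "assignment of eligible patients will be made on an alternating basis, with cohort assignment made by the CRO overseeing the study". The CRO makes the assignment "independent of investigator input and based strictly on chronology of verification of eligibility of patients as they complete screening assessments". The same rule appears in the Synopsis (Guidelines for Cohort Assignment), the Study Schema Summary, Protocol 5.1 and SAP 4.4. None of them mentions randomisation between cohorts.

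**Timing.** Alternation covers only the overlap. Cohort A can start alone: "expansion Cohort A will open to enrollment once that dose level is judged to be safe". Under Protocol 7.1 the cohort is assigned after the site sends the completed form for an eligible patient.

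**Masking and shared information.** Protocol 8.4: "This is an open-label study; study treatments will not be blinded". Under Protocol 13.8, investigators, site staff and the sponsor meet regularly to "review the status of all active patients on study"; in the expansion the calls begin at two-week intervals. Response is investigator-assessed (SAP 8.1).

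**Use of the cohorts.** Protocol 3.4 says a high and a low dose are studied "with the goal of identifying the optimal combination for subsequent clinical evaluations". Protocol 12.1.2 gives each cohort its own Simon rule against a 10% response rate, and success in either cohort is enough. SAP 8 makes all efficacy analyses descriptive.

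**Later change.** SAP 4.3.2 reports that Cohort B was closed after its 18 Stage 1 patients because of Grade 3 or 4 thrombocytopenia, and that the remaining 13 went to a new Cohort C without a Simon rule. The SAP gives no rule for allocating between A and C.

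**The concern.** Alternation is deterministic: once one assignment is known, so are all later ones. Having the CRO assign prevents an investigator from naming a cohort, but it does not hide the order; strict chronology is what makes the order readable. A site also has some control over chronology, because it decides whom to screen, when to finish assessments within the 28-day screening window and when to send the form.

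If patients with better or worse prospects were timed towards one dose, the cohorts would differ in case mix. Eligible patients do vary: ECOG 0 or 1, and no prior regimen or one. Protocol 6.7 itself warns that heterogeneity may affect interpretation, and assignment is not stratified. A case-mix difference could then be read as a dose difference when the optimal combination is chosen. It could also move a cohort across the thresholds of 2 of 18 or 5 of 31, where one response can decide the result.

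**Working it through.** **1. The plan's own design.** Inputs (Protocol 12.1.2): 18 patients in Stage 1; continue with at least 2 responses; 13 more; success with at least 5 of 31; rates 10% and 25%.

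P(success) = sum over x = 2 to 18 of Bin(x; 18, p) × P[Bin(13, p) ≥ 5 − x].

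- p = 0.10: 0.182, within the 0.20 limit.
- p = 0.25: 0.902, matching the stated 90%.
- Early stopping at 10%: 0.9^18 + 18 × 0.1 × 0.9^17 = 0.150 + 0.300 = 0.450. Expected size: 18 + 13 × 0.550 = 25.1.

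The design reproduces. Nothing in the formula refers to the other cohort, so changing how patients are split between A and B leaves these figures as they are.

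**2. Predictability with full knowledge of earlier assignments.** The guesser always names the cohort with fewer patients so far. Block sizes are assumptions; the results are from 20,000 simulated sequences of 36 assignments.

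| Scheme | Correct guesses |
|---|---|
| Alternation, after the first patient | 100% |
| Permuted blocks of 4 | 71% |
| Blocks of 4 and 6, chosen at random | 69% |
| Simple randomisation | 50% |

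Check: for a block of size 2m the expected number of correct guesses is m + (4^m / C(2m, m) − 1)/2. For m = 2: 2 + (16/6 − 1)/2 = 2.83, and 2.83/4 = 71%. For m = 3: 3 + (64/20 − 1)/2 = 4.1, and 4.1/6 = 68%.

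**3. Predictability with partial knowledge under alternation.** Suppose assignments were learned only on the two-week calls. The Synopsis plans about 80 patients in 18 months. Taking 18 months as 78 weeks gives 39 intervals and 80/39 = 2.05 patients per interval. That rate counts all enrolment, so it is high for the A/B sequence alone. With Poisson arrivals (an assumption), the average chance of a correct guess is 1/2 + (1 − e^(−2 × 2.05))/(4 × 2.05) = 0.50 + 0.12 = 62%. A slower A/B rate or contact between calls would raise it. This is not like for like with the full-knowledge figures in step 2.

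**4. What imbalance could do.** Illustration with assumed response rates of 35% (good prognosis) and 15% (poor) at both doses. The spurious difference is the difference in good-prognosis share × 20 points:

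- 60% v 40%: 0.2 × 20 = 4 points
- 70% v 30%: 0.4 × 20 = 8 points
- 80% v 20%: 0.6 × 20 = 12 points

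**5. How many patients were alternated.** With Cohort B closed at 18, there are at most 18 A/B pairs, or 36 patients. If Cohort A reached 31 (an assumption), at least 31 − 18 = 13 of its patients lie outside the A/B alternation.

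**6. Strength of an A-versus-B contrast.** For 10% v 25% at two-sided 0.05, power is 34% with 31 per arm and 21% with 18 per arm.

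**The case against.** **No comparison is planned.** Each cohort is judged alone against 10%, efficacy is descriptive, and the sample size aims at an estimate for planning later studies. This stands as far as formal inference goes. A reader might infer that alternation biases a planned dose test or spoils the Simon error rates; the documents contain no such test, and step 1 shows the error rates do not depend on the split. But choosing an optimal combination from two doses is still a comparison, and low power does not make a biased contrast safer to read.

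**There is a safeguard, and up to 20 sites share the sequence** (Synopsis: "Up to 20 centers in the US"). A site would need the latest assignment elsewhere, and Protocol 13.8 does not say that cohort assignments are disclosed on the calls. This stands: 100% is the full-knowledge figure, not a description of what sites will know.

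**Steering is hypothetical.** A reader might reason that moving three likely responders shifts a cohort's response rate by 3/31 = 9.7 points, against a design difference of 15. Nothing in the documents shows that responders can be picked out in advance, and the 15 points are 25% against the assumed doxorubicin rate of 10%, not A against B.

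**Randomisation would not fix the calendar-time gap.** Correct. That gap comes from Cohort A opening first, and only the analysis can deal with it.

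**It is too late for A versus B.** For patients already assigned, yes. The recorded closure of Cohort B also rested on thrombocytopenia, not on a response comparison with A.

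**Conclusion.** The point holds for the overlap period. Allocation there is deterministic in an open-label, investigator-assessed trial, and the CRO safeguard blocks choice of cohort without concealing the sequence. With full knowledge of earlier assignments, the next is certain under alternation and guessed about 69% of the time under assumed random blocks of 4 and 6. Under the assumed response rates, case-mix splits of 60/40 to 80/20 would produce spurious differences of 4 to 12 points.

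The documents do not support the stronger readings that both cohorts are filled entirely by alternation, that sites will know each assignment, that selection has occurred, or that a formal dose test is compromised. Randomising between cohorts would also not make either one more comparable with the 10% reference. This is a modest design weakness with an inexpensive remedy. With Cohort B closed, the part that can still act on existing data is how the SAP presents A against B.

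**What to change.** **Protocol.** In 7.2, and in the matching text of the Synopsis, Study Schema Summary, Protocol 5.1 and SAP 4.4, replace alternation with central 1:1 randomisation by the same CRO, in permuted blocks of varying, undisclosed size, whenever two expansion cohorts are open.

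**SAP.** In Section 8:

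- Base any side-by-side A-versus-B statement on patients enrolled while both cohorts were open.
- Label other Cohort A patients non-concurrent and show them separately.
- Describe the allocation as non-randomised.
- State how patients were allocated between A and C if both were open together.

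Before any display by dose, reconcile SAP 4.3.2 (Cohort B at 2 mg/kg, Cohort C at 1 mg/kg) with SAP 6.1, which lists the two the other way round.

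**Cost.** No added patients and no change to the Simon design. It needs a randomisation list, amended wording and acceptance of cohort sizes that are unequal for short periods. The documents give no operational cost, so it should not be called free. The concurrent-only comparison rests on at most 36 patients and will be imprecise.
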